#### 7.2 **Software Version**

All analyses and datasets will be programmed using Statistical Analysis Software Version 9.4 or higher. R Version 4.1.3 or higher may be used to generate data visualizations as needed.

Statistical Analysis Plan: AEGR-734-401: A 36-Month, Multicenter, Open Label Phase 4 Study to Evaluate the Document: Immunogenicity of Daily SC Metreleptin Treatment in Patients with Generalized Lipodystrophy Author: [name], [name], [name], [name] Version Number: 2.1

Page 14 of 25

Statistical Analysis Plan

#### 8. STATISTICAL CONSIDERATIONS

### 8.1 Statistical Summaries, Tests and Confidence Intervals

There will be no hypothesis testing. All data will be summarized by descriptive statistics and/or listings. Number of patients with missing data will be reported where applicable. Continuous variables will be summarized by mean, standard deviation, median, minimum, and maximum. Categorical variables will be summarized by frequency counts and percentages of each category. Missing values will be excluded from percentage calculations. Where appropriate, two-sided, 90% and 80% Clopper-Pearson exact confidence intervals (CIs) will be included as well.

## 8.2 Missing data

Generally, missing data will not be imputed. As applicable, partial dates may be imputed for the purposes of categorizing medications as prior/concomitant and defining treatment emergent adverse events (TEAEs). Partial date handling is described in **Appendix 1**. Imputed dates will NOT be presented in listings. Where applicable, counts of missing observations will be reported.

#### 9. OUTPUT PRESENTATIONS

The shell document provided with this SAP describes the presentations for this study and therefore the format and content of the summary tables, listings and figures (TLFs) to be provided by IQVIA RWES Biostatistics.

In addition to the below described analyses, other data visualizations may be generated as needed to further evaluate variables and endpoints of interest. All additional data visualizations generated will be included in the TLFs.

### 10. DISPOSITION AND DISCONTINUATIONS

Subject disposition and discontinuations will be presented for all enrolled patients (FAS). The following will be summarized: patients screened (FAS), patients receiving at least one dose of Metreleptin (SAF), patients valid for the EAS, patients completing the study, discontinuations, reasons for discontinuation, and total study participation in years. See **Section 8.1** Statistical Summaries, Tests and Confidence Intervals for a description of statistics to be reported.

Document: Statistical Analysis Plan: AEGR-734-401: A 36-Month, Multicenter, Open Label Phase 4 Study to Evaluate the

Immunogenicity of Daily SC Metreleptin Treatment in Patients with Generalized Lipodystrophy

Author: [name], [name], [name], [name] Version Number: 2.1

Page 15 of 25

Statistical Analysis Plan

#### 10.1 Derivations

 Study participation duration (years) = [(end of study date – informed consent date + 1)/365.25].

#### 11. DEMOGRAPHIC AND OTHER CHARACTERISTICS

Demographic data and other baseline characteristics will be presented for the SAF. The following demographic and other baseline characteristics will be reported for this study. See **Section 8.1** Statistical Summaries, Tests and Confidence Intervals for a description of statistics to be reported.

- Age at informed consent (years)
- Sex
- Ethnicity
- Race
- Participation in Metreleptin Effectiveness and Safety Registry (MEASuRE)

Note: MEASuRE a sister study by the same Sponsor designed to evaluate the long-term safety and effectiveness of metreleptin under normal conditions of clinical practice.

#### 11.1 Derivations

• Age at informed consent (years) = [(date of informed consent signature – date of birth + 1) / 365.25].

#### 12. MEDICAL HISTORY CONDITIONS AND SURGERIES

Medical History information will be presented for the SAF. Medical History conditions and surgeries are captured in the "Medical History" CRF. Conditions will be presented based on CRF categories. Medical History captured as "Other, specify" on the CRF will be coded using the latest version of the Medical Dictionary for Regulatory Activities (MedDRA) at time of locked database and presented in terms of system organ class (SOC) and preferred term (PT).

Additional details about lipodystrophy diagnosis will also be summarized:

- Age at lipodystrophy diagnosis
- Lipodystrophy subtype

Document: Statistical Analysis Plan: AEGR-734-401: A 36-Month, Multicenter, Open Label Phase 4 Study to Evaluate the

Immunogenicity of Daily SC Metreleptin Treatment in Patients with Generalized Lipodystrophy

Author: [name], [name], [name], [name] Version Number: 2.1

See **Section 8.1** Statistical Summaries, Tests and Confidence Intervals for a description of statistics to be reported.

#### 12.1 Derivations

• Age at lipodystrophy diagnosis (years) = [(date of lipodystrophy diagnosis - date of birth + 1) / 365.25].

#### 13. MEDICATIONS

Medications will be presented for the SAF and coded using the latest version of the World Health Organization Drug Dictionary (WHO-DD) at database lock. Medications will be categorized as prior or concomitant, and the total number of patients in each category will be summarized by anatomic therapeutic class level 3 and preferred name.

If it is unclear whether or not a medication is prior or concomitant due to partial dates, the worst case will be assumed (i.e., concomitant). See **Appendix 1** for handling of partial dates.

- 'Prior' medications are medications which the patient started and stopped prior to the first dose of study medication.
- 'Concomitant' medications are medications which:
  - O Started prior to, on or after the first dose of study medication and started no later than 14 days following end of study medication,
  - AND ended on or after the date of first dose of study medication or were ongoing at the end of the study.

See **Section 8.1** Statistical Summaries, Tests and Confidence Intervals for a description of statistics to be reported.

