4.11 Discontinuation of Metreleptin

Patients may be discontinued from metreleptin in the following situations:

- Patient decision. The patient is, at any time, free to discontinue treatment, without prejudice to further treatment.
- Investigator decision due to an AE.

Confidential Page 23 of 60

• Investigator decision due to severe noncompliance.

Patients should be encouraged to continue in the study and attend all protocol-specified visits until the end of the 3-year study period, even if discontinued from metreleptin, to enable continued evaluation of immunogenicity.

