9.7.1 Other Concomitant Treatment

Unless excluded (Section 4.4), medication considered necessary for the patient's safety and well-being may be given at the discretion of the Investigator and should recorded in the appropriate sections of the eCRF. Special attention should be paid to recording changes to the patient's anti-diabetic of lipid lowering treatments as these modifications may affect efficacy determination.

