#### 17.1 Adverse Events

Adverse Events (AEs) will be coded using the latest version of MedDRA, and summarized by SOC, preferred name, and intensity. Intensity is captured in the CRF. See **Section 8.1** Statistical Tests and Confidence Intervals for a description of summaries to be reported.

Adverse Events of Special Interest (AESIs) are defined as:

- The presence of Category D or E *in vitro* cell-based NAb activity (or the relevant corresponding test result from the ligand-binding method) to metreleptin
- Necrotizing pancreatitis
- Hepatic adverse events including potential drug induced liver injury (DILI)
- Severe hypoglycemia
- Severe hypersensitivity reactions
- New diagnoses of autoimmune disorders (for instance, autoimmune hepatitis, glomerulonephritis, lupus erythematosus, antiphospholipid antibody syndrome, rheumatoid arthritis)
- Autoimmune disease exacerbation
- Serious infection resulting in hospitalization
- All cancers (excluding non-melanoma skin cancer) by cancer type
- Exposed pregnancies and pregnancy outcomes.

TEAEs are defined as AEs that started or worsened in severity on or after the first dose of study medication. If it is unclear whether or not an AE is a TEAE due to partial dates, the worst case will be assumed (i.e., TEAE). See **Appendix 1** for handling of partial dates.

AEs, serious AEs (SAEs), AEs of special interest (AESIs), TEAEs, AEs possibly caused by metreleptin, and AEs leading to metreleptin discontinuation will be summarized by ADA positivity and titer, cell-based NAb positivity and titer, and RB positivity, titer, and quintile of percent

Document: Statistical Analysis Plan: AEGR-734-401: A 36-Month, Multicenter, Open Label Phase 4 Study to Evaluate the

Immunogenicity of Daily SC Metreleptin Treatment in Patients with Generalized Lipodystrophy

Author: [name], [name], [name], [name] Version Number: 2.1

inhibition. For each patient, only one event of each type will be selected to include in summary outputs. If a patient has multiple events the same type, the event with the highest severity level is selected. For patients with multiple events of the same type and severity, the event corresponding to the highest titer or percent inhibition level is selected. The corresponding titer and percent inhibition level are defined by the most recent measurement occurring prior to the event start date.

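### SAP 13 has no category for a drug started more than 14 days after the end of metreleptin, so such starts are left out of the medication summary (minor reporting gap)

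*SAP*

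**What the plan says.** SAP 13 states: "Medications will be categorized as prior or concomitant, and the total number of patients in each category will be summarized", by ATC level 3 and preferred name, in the safety set. It gives two definitions.

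- Prior drugs are those the patient "started and stopped prior to the first dose of study medication".
- Concomitant drugs must meet two conditions. The first allows a start before, on or after the first dose, provided the drug "started no later than 14 days following end of study medication". The second, joined to it, reads "AND ended on or after the date of first dose of study medication or were ongoing at the end of the study".

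There is no third category. When partial dates leave the choice unclear, SAP 13 and SAP Appendix 1 assume concomitant.

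Follow-up does not end with treatment. Protocol 4.11 encourages patients to "attend all protocol-specified visits until the end of the 3-year study period, even if discontinued from metreleptin". Protocol 6.4 repeats this for patients with neutralizing activity. SAP 14 repeats the general rule and notes that metreleptin may be restarted at any time in the three years.

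Protocol Table 1 reviews lipid-lowering, antidiabetic and immunomodulatory agents at every visit from Screening to Month 36. Protocol 9.7.1 asks for particular care in recording changes to antidiabetic and lipid-lowering treatment, "as these modifications may affect efficacy determination".

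**The concern.** A limit of 14 days after treatment suits a trial in which follow-up ends soon after the last dose. Here a patient can be off metreleptin and on study for many months, and the outcome rules have no matching limit. SAP 17.1 says "TEAEs are defined as AEs that started or worsened in severity on or after the first dose of study medication", with no upper bound. The by-visit summaries in SAP 15.2 and 18.2 are not restricted to time on treatment. The last analysis window is open-ended (from Day 927 in SAP Appendix 2, from Day 1003 in the later change note).

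Off-treatment visits and events therefore stay in the results, while drugs first started in the same period leave the medication summary. A new antidiabetic or lipid-lowering drug matters there for the reason Protocol 9.7.1 gives. A new immunomodulator matters in an antibody study whose entry criteria exclude patients receiving one. What is at stake is the completeness of a descriptive table that readers would use as background to the HbA1c, triglyceride and antibody results.

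**Working it through.** The plan states no figure on this point, so there is none to reproduce. The check applies the two definitions literally and then measures the period they leave uncovered.

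**Inputs.** First dose is Day 0 (SAP Appendix 2). Scheduled days are floor(30.4 × month) (SAP modification history, version 2.1), so Month 36 is floor(1094.4) = Day 1094. The stop months are assumptions, because the documents give no discontinuation times.

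**Rules.** Let S be the drug's start day, E its stop day and L the end of metreleptin.

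- Prior: S < 0 and E < 0.
- Concomitant: S ≤ L + 14, and E ≥ 0 or ongoing.

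**Coverage.** If S ≤ L + 14, the drug either ended before Day 0 (prior) or did not (concomitant), so it is always classified. If S ≥ L + 15, then S > 0 rules out prior and the 14-day limit rules out concomitant. Running through start and stop days for L = Day 364 (Month 12) confirmed this without exception: a start on Day 378 is concomitant, and a start on Day 379 or Day 700 is neither.

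**Length of the uncovered period.** Unclassifiable start days = 1094 − (L + 14).

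| Assumed permanent stop | L | L + 14 | Unclassifiable days | Share of 1094 |
|---|---|---|---|---|
| Month 6 | 182 | 196 | 898 | 82% |
| Month 12 | 364 | 378 | 716 | 65% |
| Month 24 | 729 | 743 | 351 | 32% |
| Month 36 | 1094 | 1108 | 0 | 0% |

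**Partial dates.** The worst-case rule does not close the gap, because a complete late start date leaves nothing unclear. It also gives an odd result. SAP Appendix 1 replaces a fully missing start date with the metreleptin start date, so a late drug with no recorded start date is counted as concomitant, while the same drug with a full date is not counted.

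**Restarts.** SAP 13 does not say which date ends study medication when a patient stops and resumes. Suppose metreleptin is interrupted at Day 364, is later resumed and ends at Day 800, and a drug starts on Day 450. Using the first stop, 450 > 364 + 14 = 378 and the drug is in neither category. Using the final dose, 450 ≤ 800 + 14 = 814 and it is concomitant.

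**The case against.** The strongest reply is that little depends on this table. SAP 13 plans one count of patients per drug class, not by visit and not linked to titer, HbA1c or triglycerides. No analysis in SAP 15 to 18 that we could read adjusts for, censors on or stratifies by medication category. A patient already counted for a drug or class remains counted, so a switch within that class leaves the class count unchanged. Limiting concomitant to the treatment period plus a short margin is a defensible use of the word. SAP 14.1 measures total exposure to the last administration, which favours the final-dose reading and keeps drugs started during an interruption. The number of affected patients may be zero.

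All of this stands, and it sets the severity. It does not remove the gap: SAP 13 promises to sort medications into two categories, and its definitions do not cover every drug recorded on study.

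Two stronger readings are tempting.

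- A reader might infer that these drugs are lost from the report. The documents do not support that. The data are still collected, SAP 8.1 provides for summaries and/or listings, and SAP 8.2 mentions listings when it discusses medication and event dates. No medication listing is promised outright, so the drugs may, rather than will, appear there.
- A reader might infer that the by-visit results are distorted, since one patient is 9% to 10% of a group of 10 or 11. That is the patient's share of the summary, not an error in it. No such figure changes under this rule.

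**Conclusion.** The point holds as a minor reporting gap. Under SAP 13, a drug with a complete start date more than 14 days after the end of metreleptin is neither prior nor concomitant and is left out of the summary counts. The omission could include off-treatment starts of antidiabetic, lipid-lowering or immunomodulatory drugs.

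The 898, 716 and 351 days show how long an omission is possible, not how often it happens. They assume a permanent stop at Month 6, 12 or 24, follow-up to Day 1094, and the final dose as the end of study medication.

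The changes we could read in the SAP change note concern the effectiveness set, the adverse event tables and the visit windows, not this definition. Parts of that note were not available to us, so a later revision of SAP 13 cannot be excluded.

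**What to change.** Keep the concomitant definition and add a third tabulated category to SAP 13: *post-treatment: started more than 14 days after the last metreleptin dose and on or before the end of study*. Summarize it by ATC level 3 and preferred name, like the other two. The three categories then cover every drug recorded on study.

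State also that, for patients who stop and restart, the end of study medication is the final administration, consistent with the total-duration formula in SAP 14.1.

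Removing the 14-day limit would also close the gap, but it would mix drugs taken with metreleptin and drugs started well after it. The separate category avoids that.

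The cost is two sentences and one more block in an existing table, with no new data. The change note records changes added after database lock, so this one can be documented there or, as SAP 2 provides for departures from the final SAP, in the study report.

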#### 14. STUDY MEDICATION EXPOSURE

The summary of study drug exposure and compliance will be based on the SAF population. According to the protocol, patients should be encouraged to continue in the study and attend all protocol-specified visits until the end of the 3-year study period, even if discontinued from metreleptin, to enable continued evaluation of immunogenicity. Patients who discontinue metreleptin may restart treatment at any time during the 3-year study period. Therefore, duration of exposure will be presented in two ways: 1) total duration of exposure, and 2) duration of exposure accounting for interruptions.

Document: Statistical Analysis Plan: AEGR-734-401: A 36-Month, Multicenter, Open Label Phase 4 Study to Evaluate the Immunogenicity of Daily SC Metreleptin Treatment in Patients with Generalized Lipodystrophy

Author: [name], [name], [name], [name] Version Number: 2.1

Version Date: 13MAR2024

Copyright © 2018 IQVIA. All rights reserved. The contents of this document are confidential and proprietary to IQVIA Holdings Inc. and its subsidiaries. Unauthorized use, disclosure or reproduction is strictly prohibited.

The following will also be summarized: dose interruptions, dose reductions, and overdoses, as appropriate. An overdose is defined as a dose of metreleptin that exceeds the maximum dose of 10 mg/day for patients >40 kg (refer to the United States prescribing information) and is recorded in the CRF.

See **Section 8.1** Statistical Summaries, Tests and Confidence Intervals for a description of statistics to be reported.

#### 14.1 Derivations

- Total duration of exposure (days) = date of last study medication administration date of first study medication administration + 1.
- Duration of exposure accounting for interruptions (days) = total duration cumulative time off medication
  - Cumulative time off medication is the sum of time off medication over all medication interruptions.
  - $\circ$  Time off medication (days) = restart date stop date 1.

#### 15. PRIMARY ANALYSIS – IMMUNOGENICITY

The primary immunogenicity analysis will be performed among the EAS. Analyses will be performed as described below. Additional data visualizations may be generated as needed.

#### 15.1 Primary Analysis Variables

The primary objective is to evaluate the immunogenicity associated with daily SC metreleptin treatment in patients with congenital or acquired generalized lipodystrophy. Immunogenicity will be described using the following variables:

- Anti-metreleptin/anti-HuL binding antibody measured by anti-drug antibody (ADA) titer
- Among ADA binding positive samples:
  - o Category of *in vitro* neutralizing antibody (NAb) activity to metreleptin measured by cell-based assay titer
  - Receptor blocking\* (RB) activity measured by electrochemiluminescence immunoassay (ECLIA)
    - Titer (dilution factor)
    - Percent inhibition at minimum required dilution (MRD)

\*Referred to in the protocol as receptor binding

Document: Statistical Analysis Plan: AEGR-734-401: A 36-Month, Multicenter, Open Label Phase 4 Study to Evaluate the Immunogenicity of Daily SC Metreleptin Treatment in Patients with Generalized Lipodystrophy

Author: [name], [name], [name], [name] Version Number: 2.1

Page 18 of 25

Statistical Analysis Plan

### 15.2 Primary Analysis Description, Derivations, and Definitions

The presence of anti-drug antibodies will be screened using an ADA binding assay, which detects antibodies to both Metreleptin and HuL, and reported as follows:

- Positive/negative for ADA binding by study visit. Positive ADA is defined as ADA binding detected at MRD (1:10 dilution factor). Both 90% and 80% two-sided Clopper-Pearson exact CIs will be presented.
- ADA binding by study visit and titer (negative [no ADA binding detected at MRD], 1:10, 1:50, 1:250, 1:1250, 1:6250, 1:31250). Dilution factors greater than 1:31250 will not be examined.
- Ever ADA positive and time to ADA positivity. Time to ADA positive result (months) = [((date of first ADA positive result date of baseline visit) + 1)/30.4].
- Peak ADA (defined as the measurement which detects ADA binding activity at the largest dilution factor) and time to peak ADA. Time to peak ADA (months) = [((date of peak ADA date of baseline visit) + 1)/30.4].

In vitro NAb activity will be measured in a cell-based assay and categorized into A, B, C, D and E categories based on titer. Categorization will be performed by IQVIA Data Management and the resulting derived data will be provided to IQVIA RWE Biostatistics. Positive/negative for NAb activity, high positive NAb activity, and NAb titer categories will be presented by study visit along with two-sided 90% and 80% Clopper-Pearson exact CIs. The titer categories are defined as follows:

- If no activity is detected upon initial testing (1:80 dilution factor) with the cell-based assay, the result is reported as category A.
- If activity is detected at the initial test concentration, the sample is retested at the same concentration (1:80 dilution factor). If no activity is detected on retest, the initial result is attributed to assay noise, and the sample is reported as category B.
- If activity is detected on both tests at MRD, the sample is diluted and retested until activity is no longer detected. Depending on the number of dilutions required to dilute NAb activity below the detectable threshold, the result is reported as follows:
  - o If no activity is detected at 1:800 dilution factor, then category C
  - o If no activity is detected at 1:8000 dilution factor, then category D
  - o If activity is detected at 1:8000 dilution factor, then category E. Dilution factors greater than 1:8000 will not be examined.

Positive NAb activity will be defined as a titer category C, D, or E result. High positive NAb activity will be defined as a a titer category D or E result. Category D and E results are considered to represent

Document: Statistical Analysis Plan: AEGR-734-401: A 36-Month, Multicenter, Open Label Phase 4 Study to Evaluate the

Immunogenicity of Daily SC Metreleptin Treatment in Patients with Generalized Lipodystrophy

Author: [name], [name], [name], [name] Version Number: 2.1

high potency NAb activity. The clinical relevance of NAb activity results in any category has not been determined, and is a topic of current investigation. The following information will be summarized:

- Ever NAb positive and time to NAb positivity. Time to NAb positivity (months) = [((date of first NAb positive result date of baseline visit) + 1)/30.4].
- Ever high NAb positive and time to high NAb positivity. Time to high NAb positivity (months) = [((date of first hight NAb positive result date of baseline visit) + 1)/30.4].
- Peak NAb (defined as the measurement which detects NAb activity at the largest dilution factor) and time to peak NAb. Time to peak NAb activity (months) = [((date of peak NAb date of baseline visit) + 1)/30.4].

RB activity of anti-metreleptin/anti-HuL will be assessed by ECLIA receptor blocking assay and reported as follows:

- Positive/negative for RB activity by study visit. Positive RB activity is defined as RB activity detected at MRD (1:6 dilution factor). Both 90% and 80% two-sided Exact CIs will be presented.
- RB activity by study visit and titer (negative [no RB activity detected at MRD], 1:6, 1:30, 1:300, 1:3000). Dilution factors greater than 1:3000 will not be examined.
- Percent inhibition at MRD by study visit
- Ever RB positive and time to RB positivity. Time to RB positivity (months) =  $[((date \ of \ first \ RB \ positive \ result date \ of \ baseline \ visit) + 1)/30.4].$
- Peak RB (defined as the measurement which detects RB activity at the largest dilution factor) and time to peak RB. Time to peak RB result (months) = [((date of peak RB date of baseline visit) + 1)/30.4].

See **Section 8.1** Statistical Summaries, Tests and Confidence Intervals for a description of statistics to be reported.

